7.4 Criteria for Withdrawal/ Discontinuation of Participants

If during the course of the study, a participant meets an exclusion criterion, he will be withdrawn from the study. Specifically, a potential rerupture of the graft will lead to exclusion of the patient. In any case of premature discontinuation of a participant, the reason will be documented in the respective eCRF.

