6.2 Study Duration and Study Schedule

Total duration of subject participation will be 5 years. Total duration of the study is expected to be 82 months. Duration of patient acquisition is hereby estimated to be 22 months. This estimate is based on the following assumptions:

- ACL-reconstruction surgeries performed monthly at the investigation site: 12
- Ratio of patients agreeing to participate: 60% (estimate based on internal data)
- Ratio of patients eligible for the study: 35% (estimate based on internal data)

The estimated patient allocation rate is therefore:

$$12/\text{month} * 0.6 * 0.35 = 2.52/\text{month}$$

Estimated duration for the acquisition of 56 patients is 22.2 months.

First-Patient-In: 07/2017

Last-Patient-Out: 04/2024

Statistics/Abstract: 12/2024

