7 STUDY POPULATION

7.1 Eligibility criteria

7.1.1 General Criteria for Eligibility

Participants fulfilling all of the following criteria are eligible for the study:

- 18 to 60 years of age at entry.
- Males and females.
- An ACL insufficiency as determined by clinical examination (positive pivot shift and/or positive Lachman test).

The presence of any of the following criteria will render the patient not eligible for the study:

- Contraindications to the class of drugs under study, e.g. known hypersensitivity or allergy to the investigational product,
- Women who are pregnant or breast feeding,
- Medical condition or comorbidity that would interfere with study participation.
- Other clinically significant concomitant disease states (e.g., renal failure, hepatic dysfunction, cardiovascular disease, etc.),
- Acute or chronic infections (i.e. osteomyelitis) in the surgical site,
- Uncontrolled metabolic diseases, such as diabetes, osteomalacia, thyroid dysfunctions,
- Long-term cortisone therapy,
- Autoimmune diseases,
- Radiotherapy,
- Heavy smokers,
- Motion disorder,
- Known or suspected non-compliance, drug or alcohol abuse,
- Inability to follow the procedures of the study, e.g. due to language problems, psychological disorders, dementia, etc. of the participant,
- Participation in another study with investigational drug within the 30 days preceding and during the present study,
- Previous enrolment into the current study,
- Enrolment of the investigator, his/her family members, employees and other dependent persons.

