7.1.2 Inclusion / Exclusion for Eligible Subjects

Eligible patients fulfilling all of the following inclusion criteria will be included into the study:

- Patient has reached skeletal maturity

- A complete ACL tear to be reconstructed using hamstring tendon autograft. The ACL injury can either be isolated or combined with one or several of the following injuries:
 - A meniscus tear that is either left untreated or treated with partial resection,
 - A small, stable meniscus tear treated with fixation, but fixation not interfering with the rehabilitation protocol,
 - Cartilage changes verified on MRI with arthroscopically determined intact surface or fissuring on the surface that do not reach subchondral bone or exceed 1.5 cm in diameter (Outerbridge grade I-III [81]).
- Harvested folded tendon (unsutured) has a diameter between 8 and 8.5mm at the end to be inserted into the femoral bone tunnel determined using a tendon thickness tester (Karl Storz).
- Tendon graft construct consists of one of the following:
 - Semitendinosus tendon quadrupled
 - Semitendinosus tendon quadrupled plus gracilis tendon doubled
 - Semitendinosus tendon doubled plus gracilis tendon doubled
- A normal joint status possibly combined with either one of the following findings:
 - A small-avulsed fragment located laterally, usually described as a Segond fracture,
 - Joint space narrowing grade 1 or osteophytes grade 1 as determined by the OARSI atlas [82].
- Informed Consent as documented by signature

Eligible patients fulfilling any of the following criteria will be excluded from the study:

- Prior fracture of the affected leg,
- Earlier major knee injury to the index knee,
- Associated posterior cruciate ligament injury or medial collateral ligament injury grade III in index knee,
- Previous or current ACL injury on contra-lateral leg,
- One of the following injuries to the index knee as visualized on MRI and/or arthroscopy:
 - An unstable longitudinal meniscus tear that requires repair and where the following treatment interferes with the standard rehabilitation protocol,
 - Bi-compartmental extensive meniscus resections,
 - A cartilage injury representing a full thickness loss with exposed subchondral bone (Outerbridge classification grade IV),
 - A total rupture of the lateral collateral ligament.
- Diameter of the tendon graft does not allow the use of the OCS (Irrespective of group allocation).

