8.7 Data Collection and Follow-up for Withdrawn Participants

For subjects who withdraw from the study prior to completion, the site will attempt to contact the subject in order to obtain safety information.

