8.8 Trial Specific Preventive Measures

In case of complications during ACL-reconstruction using the investigational product, the standard technique will be applied. The patient will be excluded from further analysis, the reason for exclusion will be recorded. Before every CT-scan, female patients will undergo pregnancy testing. Female patients of child bearing potential will have agreed in the informed consent form, to use contraception during the first 24 months of the study.

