9.3.7 Follow-up 5 (Visit 7)

At Follow-up 5 no CT-scan and no plain radiography will be performed. Patient-completed questionnaires and clinical examination will be done equivalently to Follow-up 2 and 3. Additionally, the study-end eCRF will be filled-out. It is scheduled 5 years after surgery.

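### Section 7.4 keeps the entry exclusion criteria in force for all 5 years, so a later pregnancy, breast-feeding or contralateral ACL injury ends a randomised patient's efficacy follow-up and may bias the later secondary comparisons

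*Combined protocol and SAP*

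**What the plan says.** Section 7.4 sets the rule: "If during the course of the study, a participant meets an exclusion criterion, he will be withdrawn from the study". The next sentence shows that it is meant to operate after surgery: "Specifically, a potential rerupture of the graft will lead to exclusion of the patient". Section 6.2 gives the period: "Total duration of subject participation will be 5 years".

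The criteria that the rule draws on include "Women who are pregnant or breast feeding" (7.1.1) and "Previous or current ACL injury on contra-lateral leg" (7.1.2). Neither is limited to entry. Section 8.6 states that no post-surgical exclusion criteria concerning compliance are defined; no other criterion is switched off after surgery.

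After withdrawal, "the site will attempt to contact the subject in order to obtain safety information" (8.7), and 9.2.6 provides a telephone interview for adverse events. Missing data are not imputed (11.5) and drop-outs are not replaced (11.6). Section 6.4 has patients told their allocation at study end, planned or not.

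The secondary analyses nevertheless run on every follow-up dataset (11.4.2.2), and the analysis is called intention-to-treat (11.4.1). Women of child-bearing potential agree "to use contraception during the first 24 months of the study" (8.8). For Visit 7, "At Follow-up 5 no CT-scan and no plain radiography will be performed" (9.3.7).

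**The concern.** Exclusion criteria normally decide who may be randomised. Here they also decide who is still followed years later. The intervention is finished on the day of surgery, so withdrawing a patient in year 3 does not remove any exposure to it. It only stops the collection of outcomes.

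Three features make the loss hard to defend:

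- **It is avoidable.** Pregnancy is no obstacle to the questionnaires and clinical tests that make up Visit 7. A contralateral ACL tear removes the reference knee for KT-1000, Lachman and pivot shift, but the index knee can still be imaged and the questionnaires can still be completed.
- **It depends on events after randomisation.** Contralateral injury plausibly falls on patients who have gone back to pivoting sport, and return to pre-injury activity is a secondary objective (4.3). Pregnancy and breast-feeding remove only women.
- **It cannot be fully repaired later.** A withdrawn patient is told the allocation (6.4), so questionnaires resumed afterwards would no longer be patient-blinded.

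At stake is the long-term clinical comparison, for which 6.1.1 itself notes the need.

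**Working it through.** **1. Does the rule reach past surgery?** Yes. It speaks of the course of the study, the study lasts 5 years per patient, and the one trigger it names, graft rerupture, can only happen after surgery. An entry-only reading does not fit the text.

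**2. The plan's own figures.** With a difference of 20%, SD 25.175%, two-sided α 0.05 and power 0.8, the normal approximation gives 25 per group. Then 50/0.9 = 55.6, so 56. Both figures in 11.2 are reproduced (the exact t calculation gives 25.87 per group, power 0.786 at 25). The secondary powers in 11.2.1 at 25 per group are also reproduced: IKDC 0.978, Lysholm 0.999, KT-1000 0.845 (with the table's effect size 0.88), Lachman above 0.99, pivot shift 0.968. The method is noncentral t, with n × 3/π for Mann-Whitney tests.

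**3. Expected withdrawals by year 5.** The documents give no rates, so these are assumptions: *w* = share of women, 30–50%; *p* = yearly rate of becoming pregnant or breast-feeding, 3–7%, counted only in the 3 years after the contraception period; *c* = yearly contralateral ACL injury rate, 0.5–1%, over 5 years.

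E = 56·w·[1 − (1 − p)³] + 56·[1 − (1 − c)⁵]

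| w, p, c | Pregnancy or breast-feeding | Contralateral ACL | Total | Share of 56 |
|---|---|---|---|---|
| 0.3, 0.03, 0.005 | 1.5 | 1.4 | 2.9 | 5% |
| 0.4, 0.05, 0.01 | 3.2 | 2.7 | 5.9 | 11% |
| 0.5, 0.07, 0.01 | 5.5 | 2.7 | 8.2 | 15% |

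**4. Expected withdrawals by year 2.** If the 24-month contraception agreement is kept, only contralateral injury counts: 56·[1 − (1 − c)²] = 0.6 to 1.1 patients.

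**5. A wider range.** With one combined yearly rate *r* for all randomised patients, 56·[1 − (1 − r)ᵀ] for r = 0.5% to 5% gives 0.6 to 5.5 by year 2 and 1.4 to 12.7 by year 5.

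**6. What is left at 5 years.** The planned 10% drop-out leaves 56 × 0.9 = 50.4. Subtracting 2.9 to 8.2 leaves 47.5 to 42.2, or about 24 to 21 per arm. At 21 per arm, power is IKDC 0.95, Lysholm above 0.99, pivot shift 0.94, Lachman above 0.99 and KT-1000 0.78. KT-1000 needs 23 per arm for 80% at effect size 0.88. The same table's 2 mm and 1.7 mm give 2/1.7 = 1.18, for which power at 21 per arm is 0.95. Even a 30% loss beyond planned drop-out leaves 35.3 patients, with IKDC power 0.91, Lysholm 0.985 and KT-1000 0.70.

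**7. The primary endpoint.** It is measured at 12 months (5.1), inside the contraception period. Contralateral injury alone at c = 1% gives 56 × 0.01 = 0.6 patients by then.

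**The case against.** The strongest reply is that the numbers are small and much of the plan limits the damage. Contraception to 24 months protects the 1- and 2-year visits from the pregnancy trigger. Section 11.5 keeps data collected before withdrawal. A 10% drop-out allowance exists, and at the low end of the assumed range the rule alone stays inside it. Patients are blinded, and there is no evident reason why pregnancy should differ by arm, so its loss mainly costs precision and generalisability. The contralateral trigger is about 1 to 3 patients over both arms. All of this stands.

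Some details of the remedy also need care. The criterion on other investigational-drug studies in 7.1.1 expressly runs during the study, so a blanket statement that every criterion ends at randomisation would contradict it. After a contralateral tear, Tegner (a whole-person activity level) and several Lysholm items name no side as printed, so those scores are not pure index-knee measures.

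A reader might go further and infer that the rule empties the 2- and 5-year comparisons, or that the stated secondary powers collapse. The documents do not support that: they contain no event rates, and on every range tried most patients remain. Nor are the later visits purely clinical comparisons: Visit 6 also has a radiograph, and adverse events are recorded at both visits.

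The reply does not make the rule harmless. Loss selected by post-randomisation events can bias a comparison even when it is small, and this loss serves no stated purpose.

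**Conclusion.** The point holds as a defect of the withdrawal rule, not as a failure of the trial. Followed as written, 7.4 stops efficacy follow-up for reasons that mostly do not prevent it, and 8.7 and 9.2.6 confirm that only safety information is sought afterwards. This conflicts with the intention-to-treat statement in 11.4.1, although that section spells out only rehabilitation non-adherence and earlier data are kept.

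The size is modest: about 3 to 8 of 56 patients by year 5 and about 1 by year 2. These figures rest on assumed rates, on the contraception agreement being kept, and on counting only pregnancy, breast-feeding and contralateral injury. Later onset of other listed conditions would add to them. The main harm is possible selection bias at 5 years; its direction and size cannot be derived from the documents. Power is secondary: only KT-1000 falls below 80%, only towards the upper end, and only at the tabulated effect size. The 12-month primary analysis is little affected. The change should be made because the lost data cannot be recovered and keeping them is cheap.

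**What to change.** Amend 7.4 to say, in substance: exclusion criteria govern eligibility up to randomisation; a randomised patient who later meets one stays in follow-up and in the analysis of the assigned arm; only assessments that cannot be done or interpreted are omitted. Then specify:

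- Imaging remains subject to the pregnancy testing already in the schedule.
- After a contralateral ACL injury, side-to-side KT-1000, Lachman and pivot-shift values are set to missing.
- IKDC, Lysholm and Tegner are still collected with the event flagged, and a sensitivity analysis leaves out post-event scores.

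Reconcile the following with the new text: the rerupture sentence in 7.4, which would otherwise still exclude the patient; the on-study wording of the other-study criterion in 7.1.1; the safety-only follow-up in 8.7 and 9.2.6; the exclusion from analysis after intra-operative complications in 8.8; and the definition of the analysis set in 11.4.1.

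The cost is one amendment, using visits already scheduled. The downside is small: a few retained patients will have partial data, or scores influenced by the other knee.

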3.4 Rationale for the Intended Purpose in Study

The clinical outcome of ACL-reconstruction depends on the successful integration of the tendon-graft into the host bone close to the attachment site of the native ACL [60-62]. The OCS is enlaced into the tendon-suture construct and provides an osteoconductive / osteoinductive environment at the articular aperture of the bone tunnel. The design maximizes the contact area between tendon and osteoconductive surface (Bone/HA). Different to the application of interference screws, graft insertion exerts minimal stress on the insert and allows the use of highly porous material. Enhanced bone-tendon integration should reduce graft micromotion and increase the repair strength of the reconstructed ACL. This in turn should reduce the rate of graft failure and the incidence of tunnel widening.

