4.3 Secondary Objectives

Secondary objectives are to assess patient subjective measures of knee function and objective measures of knee stability of the interventional treatment compared to the control treatment. Also the success of return to pre-injury activity level will be assessed. Additionally OCS-bone integration will be investigated.

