9.2.6 Assessments in Participants Who Prematurely Stop the Study

Study subjects who withdraw consent to participate or who fail to appear to the scheduled visits will be contacted by telephone in order to obtain the interview for self-reported AEs.

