11.4.1 Datasets to be analyzed, analysis populations

Statistical analysis is based on the intention-to-treat analysis. In the case of the current trial this means that patients not following the rehabilitation protocol will not be excluded from analysis.

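### Section 7.4 withdraws patients whose graft re-ruptures, so later stability, function and activity comparisons cover intact grafts only, and a rerupture before Visit 5 also loses the primary CT

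*Combined protocol and SAP*

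**What the plan says.** Section 7.4 provides that if "a participant meets an exclusion criterion, he will be withdrawn from the study", and then singles out graft failure: "Specifically, a potential rerupture of the graft will lead to exclusion of the patient".

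For withdrawn patients, Section 8.7 says that "the site will attempt to contact the subject in order to obtain safety information". Section 9.2.6, on those who withdraw consent or miss visits, says that they "will be contacted by telephone in order to obtain the interview for self-reported AEs". Neither section provides for knee tests, questionnaires or CT. Section 11.5 uses no imputation, but it does use whatever data a subject has.

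On the analysis set, Section 11.4.1 says: "Statistical analysis is based on the intention-to-treat analysis". It explains that for this trial this means that "patients not following the rehabilitation protocol will not be excluded from analysis". Graft failure is not mentioned.

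Section 3.4 says of better integration and less micromotion: "This in turn should reduce the rate of graft failure and the incidence of tunnel widening". Section 4.3 says: "Secondary objectives are to assess patient subjective measures of knee function and objective measures of knee stability", intervention against control. Sections 11.4.2.2 to 11.4.2.5 apply those comparisons (IKDC, Lysholm, KT-1000, Lachman, pivot shift, Tegner) to every follow-up dataset and give no rule for a failed graft. Graft rupture is listed as a health hazard in 10.1.1. Section 11.4.6 tabulates adverse events by arm without inference.

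**The concern.** Rerupture happens after randomisation, and the plan itself expects the device to change how often it happens. Section 3.6 also considers the opposite direction: the scaffold might speed up fatigue failure of the construct, although the bench comparison showed no such effect. Withdrawing patients because the graft failed takes the failed knees out of the outcomes meant to show whether the reconstruction holds.

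Two distortions can follow if the arms differ in reruptures:

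- **A hidden deficit.** Ruptured knees would normally pull down their arm's stability and function results. Under 7.4 they contribute nothing after the event, so an arm with more failures does not pay for them, and an arm with fewer gets no credit in these comparisons.
- **A reversal.** If the knees that fail were already the laxer ones, the survivors in the arm with more failures are a better-selected group and can look tighter than the other arm.

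A rerupture before the 1-year visit also removes the patient from the primary analysis, because no Visit 5 CT is taken after withdrawal.

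**Working it through.** **1. Which data are lost.** Follow-up visits are at 6 weeks, 4.5 months, 1, 2 and 5 years, with CT at surgery, 4.5 months and 1 year. A patient who re-ruptures at month 8, for example, has the first two follow-up visits and the 4.5-month CT. That patient has no primary CT and no stability, questionnaire or Tegner data at 1, 2 or 5 years. Section 11.5 allows the earlier visits to be used. By contrast, Section 8.8 (intraoperative complications) says explicitly that the patient leaves the analysis; 7.4 does not.

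**2. The plan's own sample size.** Inputs (11.2): difference 20, SD 25.175, two-sided alpha 0.05, power 0.80.

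n per arm = 2 × (1.960 + 0.842)² × 25.175² / 20² = 24.87, so 25. With 10% drop-out, 25 / 0.9 = 27.8, so 28 per arm and 56 in total. This agrees with the plan.

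If 3, 4 or 6 patients were lost from each arm, normal-approximation power for the primary outcome would be 0.80, 0.79 or 0.75. Power is the lesser issue.

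**3. Hidden deficit (assumed rates).** The documents give neither a rerupture rate nor the laxity of a ruptured graft. Assume 28 per arm, intact grafts equal in both arms, and ruptured grafts L = 3 to 7 mm laxer. With failures kept in, the mean difference against the arm with more failures is (r1 − r0) × L:

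| Reruptures | r1 − r0 | Difference with failures kept | Difference under 7.4 |
|---|---|---|---|
| 3 v 1 | 2/28 | 0.21 to 0.50 mm | 0 |
| 4 v 1 | 3/28 | 0.32 to 0.75 mm | 0 |
| 6 v 2 | 4/28 | 0.43 to 1.00 mm | 0 |

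**4. Possible reversal (extreme case).** Assume equal true laxity, SD 1.7 mm (11.2.1), and that the laxest knees are exactly those that rupture. Removing the upper fraction f of a normal distribution lowers the mean by SD × φ(z) / (1 − f), where z is the 1 − f quantile:

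- f = 1/28: 1.7 × 0.0786 / 0.9643 = 0.14 mm
- f = 2/28: 1.7 × 0.1364 / 0.9286 = 0.25 mm
- f = 3/28: 1.7 × 0.1845 / 0.8929 = 0.35 mm
- f = 4/28: 1.7 × 0.2256 / 0.8571 = 0.45 mm
- f = 6/28: 1.7 × 0.2916 / 0.7857 = 0.63 mm

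The arm with more failures is favoured by 0.21 mm (3 v 1), 0.31 mm (4 v 1) or 0.38 mm (6 v 2). In simulation it has the better observed mean in about 68%, 75% and 79% of trials. With the failures kept in and made 3 mm laxer, those figures are 32%, 24% and 17%.

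**5. How far this depends on the laxity–rupture link.** Simulation at 4 v 1, readings rounded to whole millimetres, planned Mann-Whitney test:

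| Correlation of laxity with rupture | Shift favouring the arm with more failures | Significant result in its favour (nominal 2.5%) |
|---|---|---|
| 1 | about 0.3 mm | about 11% |
| 0.5 | 0.15 mm | about 5% |
| 0 | about 0 mm | about 2.6% |

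**6. Would the adverse-event tables reveal it?** Fisher's exact p for 3 v 1, 4 v 1 and 6 v 2 in 28 per arm is 0.61, 0.35 and 0.25. The counts would be visible, but they would not settle whether the arms differ.

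**The case against.** The strongest reply is that the confirmatory test is CT tunnel volume at 12 months, while most of the selection falls on secondary outcomes. The illustrative reversal is also modest: 0.31 mm is about 15% of the 2 mm planning difference and less than one standard error (1.7 × √(2/28) = 0.45 mm), on a device read in whole millimetres. No section links earlier laxity to rerupture. All of this stands, and it limits what can be said about size.

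Ruptures are not concealed either. The reason for discontinuation is documented, safety contact continues, and events are tabulated by arm. That stands too, but a descriptive count does not repair the stability comparison printed beside it.

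Some stronger readings are tempting but not supported:

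- *That 7.4 contradicts the intention-to-treat statement.* Section 11.4.1 spells the term out only for rehabilitation non-compliance and is silent on graft failure. The rule departs from the principle the plan invokes, but the text of 11.4.1 is incomplete rather than contradicted.
- *That mere suspicion of a rupture triggers removal.* The word *potential* may only mean *any that occurs*; Section 9.3.3 uses it that way for adverse events. The wording is unclear, no more.
- *That all of a patient's data are discarded.* Section 11.5 supports keeping visits before the rupture.
- *That the arm with more failures will look better.* That needs the worse knees to be the ones that fail. Without that link, the rule hides a deficit but does not reverse it.

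**Conclusion.** The point holds in this form. As written, stability, function and activity comparisons at visits after a rerupture are restricted to intact grafts, and a rerupture before Visit 5 removes the primary CT. No other section brings these patients back. Because Section 3.4 expects the device to change graft failure, the restriction is not neutral between arms, and the secondary objective is not answered for the groups as randomised.

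The size is uncertain. Under the assumed 3 v 1 to 6 v 2 reruptures, and ruptured grafts 3 to 7 mm laxer, the rule hides a KT-1000 deficit of about 0.2 to 1.0 mm. A reversal of about 0.2 to 0.3 mm (3 v 1 or 4 v 1) needs a perfect link between laxity and rupture, and shrinks to about zero without one. If reruptures are few and balanced, little is lost. The case for acting does not rest on the illustration: follow-up not collected after withdrawal cannot be recovered later.

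**What to change.** Delete the rerupture exclusion in 7.4. State that these patients stay in scheduled follow-up through Visit 7, unless they withdraw consent, and are analysed in their randomised arm. Extend 11.4.1 to say so. Then prespecify:

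- **Questionnaires and Tegner:** use observed scores.
- **Stability tests:** collect observed values, and state how data after rupture or revision enter the Mann-Whitney tests. One option is worst rank from confirmed rupture until any revision, with a sensitivity analysis on observed values. Carrying worst rank through 5 years for a revised knee is a debatable choice of estimand, so the choice should be explicit.
- **Descriptive summaries:** Section 11.4.2.4 reports KT-1000 as mean and SD, and Lachman and pivot shift as frequencies. A worst rank supplies neither, so base these on observed values and print the number of ruptures by arm beside them.
- **Tunnel volume:** use scheduled CTs obtained before any revision drilling, and report how many are unavailable by arm.
- **Graft rupture:** define confirmed rupture and report it by arm, with a 95% CI for the difference.
- **Intact grafts:** show that analysis as supportive.

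The cost is a short amendment, with no new visits or procedures beyond the existing schedule. The drawback is that scores after a rupture may partly reflect revision surgery, which is why the supportive intact-graft analysis is worth keeping.
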